1.3.4 Exploratory Endpoints

- Change of the weekly average of at-home BP from Baseline to each scheduled, post-baseline visit
- Change and percent change of angiotensin II, renin (Plasma renin activity [PRA]; active renin mass concentration [ARC]), and plasma aldosterone from Baseline to each scheduled, post-baseline visit
- Percentage of subjects reaching the goals of in-clinic SBP \leq 140 mmHg, DBP \leq 90 mmHg, and both over time
- Percentage of subjects and time to requiring antihypertensive therapy during the study
- Assessments of urinary analytes (e.g., cortisol, aldosterone, angiotensin II, albumin, creatinine, protein and sodium) from Baseline to each scheduled, post-baseline visit may be performed
- PK parameters including but not limited to C_{max} (maximum observed ISIS 757456 plasma concentration), T_{max} (time to maximal plasma concentration) and AUC (area under the plasma concentration time profile for ISIS 757456)
- Potential exposure-response analysis using relevant exposure parameters and biomarkers including, but not limited to C_{trough} and plasma AGT may be performed

2 PROCEDURES

2.1 General Overview of Procedures

Ionis Pharmaceuticals, Inc. (or designee) will review all study data including source documents, case report forms, and laboratory reports. The study site will enter subject source data into the case report form. Some laboratory data will be transferred electronically from PPD Development (plasma PK) to Ionis Pharmaceuticals, Inc.

2.2 Randomization

Subjects will be randomized after all screening, run-in, and WO assessments through Study Day -7 have been completed and after the Investigator has verified that they are eligible per criteria in protocol Sections 5.1 and 5.2 and after approval reviewed by Sponsor Medical Monitor or designee. No subject may begin treatment prior to randomization and assignment of a unique subject identification number.

Eligible subjects will be stratified based on a screening plasma AGT concentration screening plasma AGT concentration ($\leq 30 \mu\text{g/mL}$ vs. $> 30 \mu\text{g/mL}$) and then subjects will be randomized 2:1 to receive ISIS 757456 or placebo as outlined in protocol Section 3.1. Eligible subjects must have a plasma AGT concentration $\geq 20 \mu\text{g/mL}$ to participate in the study (see protocol Section 5.1 Inclusion Criteria). The Sponsor or designee will prepare the randomization list and utilize an automated IRT (Interactive Response Technology) system.

2.3 Conduct

The study will be conducted in accordance with current Good Clinical Practice (GCP) and International Conference on Harmonization (ICH) guidelines, the World Medical Association Declaration of Helsinki guidelines, the Food and Drug Administration (FDA) Code of Federal Regulations, and all other local regulatory requirements.

2.4 Data Monitoring

2.4.1 Safety Data Monitoring

Ionis Pharmaceuticals, Inc. (or designee) is responsible for processing all reported adverse events (AEs). All serious adverse events (SAEs), reported to Ionis Pharmaceuticals, Inc. (or designee), are reviewed according to standard operating procedures. The medical monitor will review all AEs and SAEs on an ongoing basis throughout the study. Ionis Pharmaceuticals, Inc. (or designee) will prepare and submit safety reports to the health authorities worldwide in accordance with local requirements. If it becomes necessary to communicate new safety information, Ionis Pharmaceuticals, Inc. (or designee) will also prepare a safety notification letter and transmit it to study site. Please refer to protocol section 8.5 for details.

2.5 Data Management

An electronic case report form (eCRF) utilizing an Electronic Data Capture (EDC) application will be used for this Study.

2.5.1 Case Report Form (CRF) Data

BioClinica (or designee) is responsible for creating the Electronic Data Capture (EDC) data entry screens, database and edit checks using definitions developed by Ionis Pharmaceuticals, Inc. Ionis Pharmaceuticals, Inc. is responsible for the review, data management querying and locking of the database.

Data are single-entered into the EDC system by the investigator site staff. Programmed edit checks (computer logic that checks the validity of the data entered and also prompts for missing data that is expected to be entered) are run and automatic queries are generated. Ionis Pharmaceuticals, Inc. reviews all data for accuracy and validity and generates additional queries in the EDC system when necessary. The data are corrected or an explanation concerning the query is provided in the EDC system. After all data are entered, reviewed (by Data Management and Clinical Development) and queried, and all queries resolved, the database is locked.

2.5.2 Laboratory Data

Ionis Pharmaceuticals, Inc. is responsible for the format of the laboratory electronic data transfers, transfer schedule and review of the clinical laboratory data. This lab data will be stored as SAS data sets or Excel files.

2.5.3 Pharmacokinetics (PK) Data

Ionis Pharmaceuticals, Inc. is responsible for the management and review of the plasma drug concentration data. Final data, which has been approved by Quality Assurance, will be stored in version-controlled repository

3 ANALYSIS PLAN

3.1 General Overview of Analyses

Descriptive summary statistics including number of subjects, mean, median, standard deviation, standard error of mean, 25th percentile, 75th percentile, minimum, and maximum for continuous variables, and counts and percentages for categorical variables will be used to summarize most data. All statistical tests will be conducted using 2-sided tests with 5% Type I error rate unless otherwise stated.

[figure not shown]
PK parameters will be summarized using include number of subjects, mean, standard deviation, coefficient of variation (CV), geometric mean, median, minimum, and maximum.

Baseline definition:

The baseline for plasma AGT will be define as the average of all values on or after Study Day -7 and prior to the first dose of Study Drug. The baseline for all other assessments will be defined as the last non-missing measurement prior to the first dose, unless otherwise specified.

Analytical visits:

Data will be summarized using the visit labels provided in the data. Multiple results with the same visit label will be averaged. Results with visit labels as "Unscheduled" will not be included in the by-visit summary tables and figures except for determining baseline and the analysis of confirmed ALT/AST category (see section 3.7.3) but will be presented in data listings.

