2. Prior to Study Day 64 in the Post-Treatment Period or in the Washout Period, should a subject's BPM exceed 170 mmHg (systolic) or 110 mmHg (diastolic) a second measurement must be done within a 30-minute period. If the subject's BP is $>$ 170 mmHg (systolic) or $>$ 110 mmHg (diastolic) within the 30-minute period, an additional BP measurement should be taken within 48 hours at the Study Center, regardless of whether the initial BP measurements were taken in clinic or at home. If the subject then experiences an additional BP measurement $>$ 170 mmHg (systolic) or $>$ 110 mmHg (diastolic) (confirmed by triplicate measurement at the Study Center), they will then be withdrawn from further blinded, randomized treatment. The subject's pre-study antihypertensive medication(s) may be added back per Investigator and Sponsor Medical Monitor judgement. The subject will continue to be followed per protocol in the study. Follow-up for subjects that screen fail due to blood pressure inclusion criteria (see Section 5.1) will not be necessary.
3. On or after Study Day 64 in the Post-Treatment Period, should a subject's BPM exceed 140 mmHg (systolic) or 90 mmHg (diastolic) a second measurement must be done within a 30-minute period. If the subject's BP is $>$ 140 mmHg (systolic) or $>$ 90 mmHg (diastolic) within the 30-minute period, an additional BP measurement should be taken within 48 hours at the Study Center, regardless of whether the initial BP measurements were taken in clinic or at home. If the subject then experiences an additional BP measurement $>$ 140 mmHg (systolic) or $>$ 90 mmHg (diastolic) (confirmed by triplicate measurement at the Study Center), the subject's pre-study antihypertensive medication(s) may be added back per Investigator and Sponsor Medical Monitor judgement. The subject will continue to be followed per protocol in the study.

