3.5.3 Exploratory Analyses

The exploratory analyses will be conducted using the PPS and FAS.

The change of the weekly average of at-home BP from Baseline to each schedule post-Baseline visit, and the change and percent change from Baseline to each schedule post-Baseline visit in angiotensin II, renin (Plasma renin activity [PRA]; active renin mass concentration [ARC]), and plasma aldosterone will be compared between ISIS 757456 80 mg group and placebo group. The data will be analyzed in a similar way to the primary analysis. For the at-home BP analysis, subsequent SBP and DBP measurements will be completely removed from this exploratory analysis once the subjects received first administration of antihypertensive therapy during the study.

The percentage of subjects reaching the following goals for the in-clinic BP over time will be summarized, comparison of which will be made between ISIS 757456 80-mg group and placebo group using Fisher's exact test. Subsequent SBP and DBP measurements will be completely removed from this exploratory analysis once the subjects received first administration of antihypertensive therapy during the study.

- Percentage of subjects reaching SBP goal of ≤ 140 mmHg
- Percentage of subjects reaching DBP goal of ≤ 90 mmHg
- Percentage of subjects reaching both goals of SBP ≤ 140 mmHg and DBP ≤ 90 mmHg

The antihypertensive therapy will be identified through medical review when database is locked. The percentage of subjects requiring antihypertensive therapy during the study will be compared between ISIS 757456 80 mg group and placebo group in PPS and FAS using Chi-Square test or Fisher's exact test as appropriate. The time in days from first dose of Study Drug to the first administration of antihypertensive therapy during the study will be summarized using the following descriptive statistics: mean, standard deviation, median, P25, P75, and minimum and maximum. The Kaplan-Meier curves [1] for time to the first administration of antihypertensive therapy will be provided for ISIS 757456 80 mg group and placebo group, comparison of which may be made statistically using the log rank test. The time to the first administration of antihypertensive therapy will be calculated as:

- [Date of the first administration of antihypertensive therapy – Date of first dose of study drug +1]

Patients who did not receive any antihypertensive therapy during the study will be censored at the date of end of study.

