3.7.4 Vital Signs

Vital signs will include heart rate, respiratory rate, body temperature, BMI and systolic and diastolic blood pressure. Vital signs will be summarized by treatment group for vital sign values as well as the change and percent change from baseline at each post-baseline visit.

The study provided at-home blood pressure monitor (Omron Device) is used to assess each at-home triplicate measurement. The device automatically conducts three successive blood pressure assessments with 60 seconds in between each measurement. The device records one time for the triplicate assessments - the time provided is the start time of the triplicate sequence, therefore, the data reported in the subject diary and in EDC has one collection time for all three blood pressure assessments. The triplicate average will be based on the first 3 blood pressure assessments.

3.7.5 12-Lead Electrocardiograms (ECG)

Safety 12 lead ECG will be performed in triplicate at the visits indicated in the protocol Schedule of Procedures. The baseline is defined as the average of the triplicate prior the first dose of study drug.

The ECG data will include ventricular rate (VR), PR interval, QRS duration, QT, and corrected QT intervals, and overall interpretation.

For the continuous variables above, descriptive statistics (n, mean, standard error, standard deviation, median, 25th percentile, 75th percentile, minimum and maximum) of the average of triplicate results at each study visit, as well as the change and percent change from Baseline to each study visit, will be presented in summary tables; for the categorical responses to overall

interpretation, the worst of triplicate results and the associated findings at each visit will be summarized by counts and percentages. All the ECG data collected in triplicate will be listed.

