5 APPENDICES

5.1 Visit window for prior-treatment visit

For the at-home blood pressure results summary, the weekly average approach is applied, which is similar to the post-baseline summary approach. If there are multiple results on the same day for a subject, the average daily values were calculated first. Daily subject values within consecutive seven-day periods are averaged to determine the subject weekly result value. The visit window is as following: subject values from Days -21 to -15, -14 to -8, and -7 to -1 inclusively represent Week -3 (Run-In), Week -2 (washout first week) and Week -1 (washout second week), respectively.

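### If the Day 64 safety repeat is stored under the scheduled visit label, the same-label averaging rule in SAP 3.1 raises in-clinic BP goal rates; the SAP should fix the visit value as the first triplicate

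*Combined protocol and SAP*

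**What the plan says.** **Repeat rule.** Protocol 8.5.3 item 3 reads: "On or after Study Day 64 in the Post-Treatment Period, should a subject's BPM exceed 140 mmHg (systolic) or 90 mmHg (diastolic"), and a second measurement must follow within 30 minutes. If that is also high, a Study Center measurement follows within 48 hours, "regardless of whether the initial BP measurements were taken in clinic or at home". During treatment (protocol 8.6.5 item 2) and post-treatment before Day 64 (8.5.3 item 2), the high-side trigger is 170/110. Item 1 of 8.5.3 also requires a repeat when SBP is 100 or lower.

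**Averaging rule.** SAP 3.1, under analytical visits: "Multiple results with the same visit label will be averaged". The next sentence adds: "Results with visit labels as 'Unscheduled' will not be included in the by-visit summary tables and figures", with exceptions for determining baseline and for confirmed ALT/AST.

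**Endpoints touched.** SAP 3.5.3: "The percentage of subjects reaching the following goals for the in-clinic BP over time will be summarized". The goals are SBP at or below 140, DBP at or below 90, and both, compared by Fisher's exact test. Change in in-clinic SBP at each scheduled visit is a secondary endpoint (SAP 1.3.2, 3.5.2).

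**In-clinic value.** Protocol 6.1.1.1 has the site document the mean of three readings. It does not say what happens to a second set. The SAP sentence "The triplicate average will be based on the first 3 blood pressure assessments" stands in the at-home device paragraph of 3.7.4 and does not cover clinic readings.

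**The concern.** Whether a visit gets a second set of readings depends on the first set, and the cut-off for repeating is the goal itself. Averaging the two sets can then move a failing visit to success, while a visit that passed by chance is not re-examined. For example, a first set of 143/88 and a repeat of 136/86 average to 139.5/87, which counts as at goal. A first set of 138/86 is never repeated, whatever a repeat would have shown.

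At stake are the absolute goal rates at Days 64, 78, 106 and 127 and, slightly, the in-clinic SBP and DBP time course, because the measurement process changes at Day 64. The result would depend on a data-entry choice that neither document makes, and sites in a multicenter study could make it differently.

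**Working it through.** The documents state no goal rate and no BP SD, so there is no figure to reproduce. The check has four steps.

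**1. Does the trigger match the endpoint?** A repeat is required if SBP > 140 or DBP > 90. Both goals are met if SBP ≤ 140 and DBP ≤ 90. Each is the exact complement of the other. A visit meeting both goals is repeated only if SBP ≤ 100, which has no practical bearing on the 140 goal. If the repeat is averaged in, the both-goals rate can therefore only rise.

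**2. A single subject (exact, SBP trigger only).** Let true SBP be 140, with independent, equal, symmetric normal errors e1 and e2 on the two sets. The visit is moved to goal if e1 > 0 and (e1 + e2)/2 ≤ 0. That region is a 45° sector of the plane: 45/360 = 1/8, or 12.5 points.

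**3. Group rates at Day 64 (simulation).** First set = truth + error. If the trigger is met, the analysed value is the mean of the two sets; otherwise it is the first set. Assumptions, none from the documents:
- mean 146/90 placebo and 138/86 active;
- between-subject SD 11/8, correlation 0.5;
- set-to-set SD 3 to 7 systolic and 3 diastolic;
- no systematic fall on the repeat.

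The repeat is taken as a full triplicate, since protocol 6.1 refers all BP assessments to the measuring instructions. With 2,000,000 draws per arm and setting:

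| Quantity | Placebo | Active |
|---|---|---|
| Repeat triggered | 78–79% | 55–56% |
| Both goals, systolic set SD 5 | 21.6% → 25.1% (+3.5) | 44.7% → 49.9% (+5.2) |
| Both goals, rise over SD 3–7 | 2.6–4.2 points | 3.9–6.3 points |
| SBP goal, net rise over SD 3–7 | 1.3–2.1 points | 2.0–4.2 points |
| Mean SBP shift, SD 5 | −0.22 mmHg | −0.27 mmHg |

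Over SD 3 to 7 the mean SBP shift is −0.1 to −0.5 mmHg. The SBP-goal rise is smaller because the trigger is systolic or diastolic: a visit with SBP at goal but DBP above 90 is also averaged, and 1.0–2.8% of visits lose the SBP goal that way. Likewise 1.8–3.0% lose the DBP goal.

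A second set of assumptions (means 135/84 to 150/92, between-subject SD 12/9, set-to-set SBP SD 3 to 8) gives a both-goals rise of 1.6 to 7.5 points.

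**4. Scale.**
- *Subjects.* About 30 subjects at 2:1 is 20 active and 10 placebo. At SD 5 the rise is 20 × 0.052 ≈ 1.0 active and 10 × 0.035 ≈ 0.4 placebo subjects.
- *Arm difference, both goals.* 44.7 − 21.6 = 23.1 points becomes 49.9 − 25.1 = 24.8, a change of 1.7.
- *Arm difference, mean SBP.* −0.27 − (−0.22) = −0.05 mmHg.
- *Before Day 64.* A reading above 170 needs a repeat below 2 × 140 − 170 = 110 to average to 140. The simulated gain is 0.0 points.
- *Unscheduled label.* The repeat is excluded and the gain is 0.

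**The case against.** The strongest reply is that the SAP may already exclude these readings. A triggered repeat is not in the Appendix A schedule, the site documents one average of three readings per visit, and results labelled Unscheduled stay out of the by-visit tables. This stands as far as it goes: a reader might infer that the goal rates are inflated, but the documents support only a conditional statement. It does not close the point, because no text assigns the label, and a repeat taken minutes later in the same visit could readily be entered under that visit.

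Second, the consequence is limited. The goal rates are exploratory, both arms move the same way, and one subject is 5 or 10 points. That stands, and it sets the weight of the point. A reader might infer a biased treatment comparison, but the calculated effect on it is small.

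Third, larger effects are easy to produce. If the second set reads 3/1.5 mmHg lower, the both-goals rise becomes 5.2–6.5 points (placebo) and 7.3–9.2 (active), and mean SBP shifts by −0.9 to −1.6 mmHg. Nothing in the documents supports such a fall. Without it, a visible artificial step in SBP at Day 64 should not be claimed.

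Fourth, protocol 3.1 and SAP 1.1 give a different post-treatment criterion: home BP above 140/100 on 2 consecutive days. The exact match to the goals rests on 8.5.3, which is where the 30-minute repeat is required.

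**Conclusion.** The gap is real and conditional. If the repeat carries the scheduled label, the Day 64 both-goals rate is biased upward by about 3 to 4 points on placebo and 4 to 6 on active. The SBP-goal rate rises by about 1 to 4 points net, and mean SBP falls by 0.1 to 0.5 mmHg. These sizes rest on assumed means and SDs and on no systematic fall. Only Day 64 was computed. At later visits, BP after restarted antihypertensives is removed (SAP 3.5.2, 3.5.3), so the analysed subjects differ.

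Two further readings do not hold. Movement is one-way for both goals only; single-component goals can also be lost. Nor need the home-BP rules conflict: 3.7.4 says how one triplicate is averaged, and Appendix 5.1 ("If there are multiple results on the same day for a subject, the average daily values were calculated first") says how several same-day results are combined. No home-BP effect was calculated.

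**What to change.** Add to SAP 3.1: for in-clinic SBP and DBP, the post-Baseline value at each scheduled visit is the mean of the first scheduled triplicate. Repeats and confirmations taken under protocol 8.5.3 or 8.6.5 are listed only and do not enter the by-visit, change-from-Baseline or goal-attainment analyses, whatever visit label they carry.

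Leave the Baseline definition (last non-missing pre-dose measurement) and the home-reading rules as they are.

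The cost is two sentences and one programming flag, with no new data and no change to safety monitoring. The small downside is that the repeat readings are not used for efficacy.

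Separately, the post-treatment add-back criteria in protocol 3.1 and SAP 1.1 (140/100 at home on 2 consecutive days) and in protocol 8.5.3 item 3 (140/90) differ and must be reconciled. The date of add-back also decides which BP values the SAP removes.

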3.3 Statistical Methods

3.3.1 Subject Populations Analyzed

The following analysis populations are defined for this study:

- Full Analysis Set (FAS): All randomized subjects who have received at least 1 injection of Study Drug (ISIS 757456 or Placebo) and who have at least 1 post-Baseline efficacy or exploratory measurements.
- Per Protocol Set (PPS): All FAS subjects who received at least 5 of the 7 doses of Study Drug, did not receive antihypertensive medications during the Treatment Period and prior to Study Day 43, and have no significant protocol deviations that would be expected to affect efficacy or exploratory assessments.

- Safety Set: All subjects who are randomized and receive at least 1 dose of Study Drug.
- PK Set: All subjects who are randomized and receive at least 1 dose of ISIS 757456 and have at least 1 evaluable PK sample.

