10.3. Populations

Full Analysis Set (FAS): All randomized subjects who have received at least 1 injection of Study Drug (ISIS 757456 or Placebo) and who have at least 1 post-Baseline efficacy or exploratory measurements.

Per Protocol Set (PPS): All FAS subjects who received at least 5 of the 7 doses of Study Drug, did not receive antihypertensive medications during the Treatment Period and prior to Study Day 43, and have no significant protocol deviations that would be expected to affect efficacy or exploratory assessments.

Safety Set: All subjects who are randomized and receive at least 1 dose of Study Drug.

PK Set: All subjects who are randomized and receive at least 1 dose of Study Drug and have at least 1 evaluable PK sample.

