10.6.4. Pharmacokinetic Analysis

The plasma PK of ISIS 757456 (total Full Length ASO, including fully conjugated, partially conjugated, and unconjugated ISIS 757456) will be assessed following SC administration. Non-compartmental PK analysis of ISIS 757456 (total Full Length ASO) will be carried out on each individual subject data set.

Other plasma PK parameters, as appropriate, may be determined or calculated at the discretion of the PK scientist.

Metabolite identification and profiling may be conducted on select plasma samples.

Plasma PK parameters will be summarized using descriptive statistics. Additional details regarding the PK analysis will be described in the Statistical Analysis Plan (SAP).

Analysis of potential exposure-response relationship between plasma AGT and ISIS 757456 exposure (such as C_{trough}) will be conducted. Relationships between other relevant biomarkers and PK measures may also be explored, if deemed appropriate.

Population PK and PK/PD analysis may be performed using PK data from this Study, and/or combined with other ISIS 757456 clinical PK/PD data later in the development timeline.

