3.6 Pharmacokinetic Analysis

The plasma pharmacokinetics of ISIS 757456 (as total full-length oligonucleotides or ISIS 757456-equivalent, ISIS 757456-eq.) will be assessed following SC administration(s). The analyses will be conducted on the PK Set.

Metabolite identification and profiling may be determined in some of the collected plasma samples and will be reported separately.

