3.6.3 Pharmacokinetic/Pharmacodynamic Exposure-Response Analysis

Exposure-response correlations maybe explored graphically between plasma exposure (AUC, C_{max} , C_{min} , as appropriate), and selected PD measures (e.g. serum AGT level), other relevant biomarkers (such as plasma renin activity, angiotensin II, etc) and relevant clinical endpoints (such as in-clinic systolic blood pressure). In addition, the relationship between serum AGT level with plasma concentrations (C_{max} , C_{min} , as appropriate) of ISIS 757456 eq. may be further evaluated with an inhibitory effect E_{max} model.

Population PK and PKPD analysis may be performed using the PK and PD data from this Study, and/or combined with other ISIS 757456 clinical PK/PD data from any previous and future studies in the development timeline.

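### With placebo subjects outside the SAP's PK Set, an exposure-response fit or plot anchored at pre-dose can credit change shared by both arms to drug concentration

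*Combined protocol and SAP*

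**What the plan says.** **Population.** SAP 3.3.1 has "PK Set: All subjects who are randomized and receive at least 1 dose of ISIS 757456 and have at least 1 evaluable PK sample". SAP 3.6 opens with "The analyses will be conducted on the PK Set", and 3.6.3, which sits under it, names no other set. Protocol 10.3 has "PK Set: All subjects who are randomized and receive at least 1 dose of Study Drug and have at least 1 evaluable PK sample", and the protocol glossary defines Study Drug as ISIS 757456 or placebo. The protocol wording can therefore admit a placebo subject, although it does not say whether a placebo sample counts as evaluable. The SAP wording cannot.

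**Status of the analysis.** SAP 3.6.3 is permissive: "Exposure-response correlations maybe explored graphically between plasma exposure" and PD measures, other biomarkers and clinical endpoints, with in-clinic SBP given as an example. One model is named, for AGT only: "the relationship between serum AGT level with plasma concentrations" of the drug "may be further evaluated with an inhibitory effect E_{max} model". The SAP gives no intercept, placebo, visit or baseline term for it. Protocol 10.6.4 is firmer: "Analysis of potential exposure-response relationship between plasma AGT and ISIS 757456 exposure" is something it says will be done, though it names no population. The exploratory endpoint in protocol 1.2.4 and SAP 1.3.4 says only that such an analysis may be performed.

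**Design.** There is one active dose level, 80 mg, against placebo, with 2:1 allocation and about 30 subjects.

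**The concern.** An exposure-response relationship needs a response at zero exposure. In a trial with one dose level, the randomized placebo arm is the only concurrent source of it. Without that arm, three sources remain, each with a weakness.

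- **Active subjects' own pre-dose values.** These differ from later values in time as well as in exposure.
- **Late follow-up.** Drug may not have cleared. For blood pressure, antihypertensives may by then have been added back. SAP 3.5.2 and 3.5.3 drop readings taken after that point from their analyses; 3.6.3 has no such rule.
- **Extrapolation below the observed exposures.** This is unbiased under the right model but imprecise.

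Pre-dose is a natural anchor for an inhibitory Emax model, because pre-dose PK and AGT samples are scheduled on Day 1. With that anchor, the fit compares before with after. A shared shift from any cause, such as a time trend, placebo response or residual effect of stopping two antihypertensives, is then mixed with concentration. PK/PD correlation is a stated exploratory objective, so the reported relationship, and any Emax or EC50 for AGT, could be distorted.

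**Working it through.** **Inputs from the documents.** About 30 subjects at 2:1 gives 30 × 2/3 = 20 active and 30 × 1/3 = 10 placebo. The plan's general test level is 5%, two-sided; 3.6.3 names no test. The documents as supplied give no figure for the exposure-response analysis, so there is none to reproduce.

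**Assumptions, not from the documents.** The true drug effect is zero. Both arms share a post-dose change δ. SBP change has δ = -5 mmHg and SD 10. AGT percent change has δ = -10 points and SD 15. Exposure c is scaled to mean 1 in the active arm, with coefficient of variation v of 0.3 or 0.6 (SBP) or 0.4 (AGT).

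**Slope per mean exposure (large-sample forms).**

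1. Active only, forced through zero change at zero exposure: δ/(1 + v²).
2. Active only, pre-dose points at zero exposure pooled with post-dose points: δ/(1 + 2v²).
3. Active only, change from Baseline at one visit, free intercept: 0, with standard error SD/(v√20).
4. Active plus placebo at zero exposure, change from Baseline, free intercept: 0, with standard error SD/√{30[(2/3)(1 + v²) − 4/9]}.
5. As 4, but pooling pre-dose and post-dose points with no visit term: 0.75δ/(1 + 1.5v²).

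For example, form 2 at v = 0.3 is -5/1.18 = -4.24. Form 3 at v = 0.3 is 10/(0.3 × 4.472) = 7.45. Form 4 at v = 0.3 is 10/√8.467 = 3.44.

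| Form | SBP, v = 0.3: formula / simulated | SBP, v = 0.6: formula / simulated | AGT, v = 0.4: formula / simulated |
|---|---|---|---|
| 1 false slope | -4.59 / -4.66 | -3.68 / -3.96 | -8.62 / -8.82 |
| 2 false slope | -4.24 / -4.34 | -2.91 / -3.28 | -7.58 / -7.89 |
| 3 slope | 0 / -0.05 | 0 / -0.16 | 0 / -0.28 |
| 3 standard error | 7.45 / 8.36 | 3.73 / 4.47 | 8.39 / 9.58 |
| 4 slope | 0 / -0.05 | 0 / -0.10 | 0 / -0.05 |
| 4 standard error | 3.44 / 3.49 | 2.69 / 2.92 | 4.78 / 4.94 |
| 5 false slope | -3.30 / -3.38 | -2.44 / -2.71 | -6.05 / -6.25 |

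Simulations used 3,000 runs per setting. They differ somewhat from the formulas because 20 skewed exposures usually show a smaller sample CV than the population value. Form 5 shows that adding placebo is not enough if visits are pooled without a visit term.

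**As an Emax fit.** Take lognormal troughs with CV 0.6, EC50 at the median trough, and no drug effect. An active-only fit anchored at pre-dose reports about 95% of the shared change as drug effect at the median trough. Its false-positive rates are:

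- SBP, SD 12: 39% at δ = -5 and 77% at δ = -8.
- AGT, SD 15: 26% at δ = -5 and 77% at δ = -10.
- AGT, SD 20: 53% at δ = -10.

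The active-only free-intercept fit at one visit gives 4.6% to 5.5%, and placebo at zero exposure with a free intercept gives 4.5% to 6.3%. For SBP, the standard deviation of the estimated effect at the median trough is about 11 mmHg for the active-only free-intercept fit and about 4 mmHg with placebo added. A repeated-visit version over seven visits from Day 1 to Day 43 gave 40% and 74% for SBP at -5 and -8 when active-only, and 4.3% to 7.7% with placebo and visit effects.

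**The case against.** The strongest reply is that the SAP does not specify the model criticised here. It gives no pre-dose anchor, and its rules setting values below quantification to zero cover descriptive statistics and PK parameters, not exposure-response. A reader might infer that any shared change will necessarily be credited to concentration. The documents do not support that: form 3 uses active subjects only and is unbiased, and the SAP does not say which form applies.

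A reader might also infer that SBP will be tested in an Emax model. It will not, on this text: 3.6.3 names that model for AGT and mentions SBP only for graphs. The SBP false-positive rates therefore illustrate the mechanism and do not describe a planned test.

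Two further inferences fail. The efficacy conclusions are not at risk, because SAP 3.5.1 and 3.5.2 compare randomized arms in the PPS, and for the secondary endpoints also in the FAS. Nor do the documents say that estimates from this fit feed later modelling; 3.6.3 says later population work may use the data.

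It is also fair that the size of any shared change is unknown. Antihypertensives stop two weeks before Day 1, and the baselines are taken late in washout or on Day 1, so residual washout may be small. Active subjects also supply data over falling exposure to Day 127. Finally, with one dose level, a model that includes placebo leans heavily on the active-placebo contrast already analysed in 3.5.2.

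What remains is that the population rule leaves out the only concurrent zero-exposure control, nothing in 3.6.3 rules out the biased form, and the unbiased active-only form is much less precise than it need be.

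**Conclusion.** The point holds as a conditional weakness in an optional, exploratory analysis. The SAP population rule and its conflict with protocol 10.3 are plain on the text. The bias depends on how 3.6.3 is carried out. If pre-dose serves as the zero-exposure anchor, roughly two thirds to nine tenths of a shared change appears as a linear concentration effect in the settings tried (-3.28/-5 = 66% to -4.66/-5 = 93%). If a free intercept is used across active subjects at one visit, there is no bias, but the SBP slope has about 1.5 to 2.4 times the standard error obtained with placebo included (4.47/2.92 and 8.36/3.49). These figures rest on assumed shared changes, SDs and exposure CVs. For AGT the distortion matters less if the drug effect is large relative to the shared change.

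**What to change.** Reconcile the PK Set wording in protocol 10.3 and SAP 3.3.1. Keep the ISIS 757456-only set for concentration summaries and non-compartmental parameters. Then add to SAP 3.6.3, in substance:

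> Any exposure-response plot or model will include FAS subjects with PD data. Active subjects enter with their measured exposure and placebo subjects with exposure zero at every visit. The response is change from Baseline, with a free placebo intercept. If visits are pooled, the model will include visit and subject effects.

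Placebo subjects should be marked on the AGT, biomarker and SBP plots, so that a reader can tell the contrast between arms from the spread of exposure within the active arm. The same edit can settle whether the AGT analysis will be done (protocol 10.6.4) or may be done (SAP 3.6.3).

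The cost is SAP wording and a small programming change. No new samples are needed, because AGT, the exploratory biomarkers and blood pressure are scheduled for all subjects. The downside is a slightly larger model and possibly a smaller apparent exposure effect.
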